Table 10: Analysis Visit Window for Proportion of Positive Pruritus Assessment.....	67
Table 11: Definition of Region Variable	68
Table 12: Heart Rate by Age (Beats/Minute) Reference	70
Table 13: Normal Respiratory Rate by Age (Breaths/Minute) Reference.....	70
Table 14: Normal Blood Pressure by Age (mm Hg) Reference	70
Table 15: Normal Temperature Range by Method	71

List of Figures

Figure 1	Study Design	16
Figure 2	Study Design for Cohort 2 as of Protocol Amendment 6	16

List of Abbreviations

Abbreviation	Definition
AE(s)	Adverse Event(s)
AFP	Alfa-fetoprotein
ALP	Alkaline Phosphatase
ALT	Alanine Aminotransferase
APRI	Aspartate Aminotransferase to Platelet Ratio Index
AST	Aspartate Aminotransferase
ATC	Anatomical Therapeutic Chemical
BMI	Body Mass Index
BRIC	Benign Recurrent Intrahepatic Cholestasis
CAP	Controlled Attenuation Parameter
CDC	Centers for Disease Control and Prevention
CDF	Cumulative Distribution Function
CI	Confidence Interval
COVID-19	Coronavirus Disease 2019
CPK	Creatine Phosphokinase
CSR	Clinical Study Report
DSMB	Data Safety and Monitoring Board
eCRF	Electronic Case Report Form
eDiary	Electronic Diary
EOT	End of Treatment
EU	European Union
FAS	Full Analysis Set
Fib-4	Fibrosis-4
GGT	Gamma-glutamyl Transferase
GIC	Global Impression of Change
GIS	Global Impression of Symptoms
ICF	Informed Consent Form

Abbreviation	Definition
ICH	International Council for Harmonisation
INR	international normalised ratio
ISE	Integrated Summary of Effectiveness
ISS	Integrated Summary of Safety
LDH	Lactate Dehydrogenase
MAA	Marketing Authorisation Application
MedDRA	Medical Dictionary for Regulatory Activities
MELD	Model for End-stage Liver Disease
NA	Not Applicable
NAPPED	Natural Course and Prognosis of PFIC and Effect of biliary Diversion
NDA	New Drug Application
ObsRO	Observer-reported Outcome
p-C4	Plasma 7 α -hydroxy-4-cholesten-3-one Concentration
PedsQL	Pediatric Quality of Life Inventory
PELD	Paediatric End-stage Liver Disease
PFIC	Progressive Familial Intrahepatic Cholestasis
PRO	Patient-reported Outcome
PT	Preferred Term
QoL	Quality of Life
RoW	Rest of World
SAE(s)	Serious Adverse Event(s)
SAP	Statistical Analysis Plan
SAS [®]	Statistical Analysis System Software
SE	Standard Error
SI	International System of Unit
SOC	System Organ Class
StdDev	Standard Deviation
T	Telephone Contact

Abbreviation **Definition**

TEAE(s)	Treatment-emergent Adverse Event(s)
TFLs	Tables, Figures, and Listings
ULN	Upper Limit of Normal
US	United States
V	Clinic Visit
VS	Visit Screening
WHO	World Health Organization

1. Introduction

The purpose of this statistical analysis plan (SAP) is to provide detailed descriptions of the statistical methods, data derivations, and data displays for Study Protocol A4250-008, *An Open-Label Extension Study to Evaluate Long-Term Efficacy and Safety of A4250 in Children with Progressive Familial Intrahepatic Cholestasis Types 1 and 2 (PEDFIC 2)*. The table of contents and templates for the tables, figures, and listings (TFLs) will be produced in a separate document.

Any deviations from this SAP will be described and justified in the clinical study report (CSR). The preparation of this SAP has been based on International Council for Harmonisation (ICH) E3 and E9 guidelines^{1,2}. All data analyses and generation of TFLs will be performed using Statistical Analysis System (SAS[®]) software (Version 9.4 or higher). The SAP will be finalised and signed off prior to locking the database.

2. Study Objectives

2.1 Primary Objectives

Cohort 1

To demonstrate a sustained effect of odevixibat (A4250) on serum bile acids and pruritus in children with progressive familial intrahepatic cholestasis (PFIC) Types 1 and 2.

Cohort 2

To evaluate the effect of odevixibat on serum bile acids and pruritus in patients with PFIC who either (1) Do not meet eligibility criteria for Study A4250-005 (PEDFIC 1) or (2) Patients who do meet the eligibility criteria for Study A4250-005 after recruitment of Study A4250-005 has been completed.

¹ ICH Topic E3: Structure and Content of Clinical Study Reports (CPMP/ICH/137/95- adopted December 1995)

² ICH Topic E9: Statistical Principles for Clinical Trials (CPMP/ICH/363/96 – adopted March 1998).

2.2 Secondary Objectives

Cohorts 1 and 2:

- To evaluate the long-term safety and tolerability of repeated daily doses of odevixibat
- To evaluate the effect of odevixibat on growth
- To evaluate the effect of odevixibat on biliary diversion and/or liver transplantation
- To evaluate the effect of odevixibat on biochemical markers of cholestasis and liver disease

3. Study Design

3.1 General Study Design

This is a Phase 3, multicentre, open-label extension study to investigate the long-term efficacy and safety of odevixibat at doses of 40 and 120 µg/kg/day in patients with PFIC, including episodic forms also referred to as benign recurrent intrahepatic cholestasis (BRIC). Cohort 1 includes children with PFIC Types 1 and 2 who have participated in Study A4250-005. Cohort 2 includes patients with any type of PFIC who have elevated serum bile acids and cholestatic pruritus and who either (1) did not meet eligibility criteria for Study A4250-005 (PEDFIC 1) or (2) were eligible for enrolment in Study A4250-005 after recruitment of Study A4250-005 completed. Up to 40 patients' post-biliary diversion surgery were allowed to participate in Cohort 2.

Study data are reviewed periodically (approximately on a quarterly basis) by a Data Safety and Monitoring Board (DSMB) until the last patient reaches 72 weeks.

Informed consent must have been obtained before any study procedures were performed. After signing the informed consent form (ICF), patients were evaluated for study eligibility and considered to be enrolled in the study. For Cohort 1, patients were eligible to participate in this extension study if they completed the 24 weeks of treatment in Study A4250-005, or, prior to amendment 6 of the A4250-005 protocol, withdrew from Study A4250-005 after a minimum of 12 weeks of treatment with odevixibat due to

patient/caregiver judgment of no improvement/intolerable symptoms but met all inclusion criteria and no exclusion criteria. Patients who withdrew from Study A4250-005 due to a study drug-related adverse event (AE) were not eligible. For Cohort 2, patients meeting all inclusion criteria and no exclusion criteria were eligible.

Before protocol amendment 6 of the A4250-008 protocol, eligible patients were enrolled into this open-label extension study and treated with a daily dose of odevixibat 120 µg/kg/day for 72 weeks. Patients not tolerating the 120 µg/kg/day dose after a minimum of 1 week had the option to down-titrate to a lower dose (40 µg/kg/day). The patient was to return to the higher dose as soon as deemed appropriate by the investigator. Under protocol amendment 6, patients entering Cohort 2 were to start treatment at 40 µg/kg/day with the possibility to dose escalate to 120 µg/kg/day after 12 weeks if there was no improvement in pruritus based on investigator judgment. The patient could return to the lower dose if the 120 µg/kg/day dose was not tolerated following a minimum of 1 week of treatment. Any dose titration was to be done in consultation with the sponsor Medical Monitor or designee. Patients who wished to continue receiving odevixibat after 72 weeks had the option to remain on treatment in an extension period with visits every 16 weeks until the drug was commercially available, provided continued use was supported by the risk-benefit profile and the patient had not been previously withdrawn or discontinued from the study. In that case the 4-week Follow-up period would not occur.

Patients in Cohort 2 went through a Screening period consisting of 2 clinic visits as follows:

[figure not shown]
- Visit S-1: Screening Visit 1 (Days -56 to -35)
- Visit S-2: Screening Visit 2 (Days -28 to -7)

Patients who did not meet eligibility criteria may have been re-screened after consultation with the Medical Monitor. Patients not fulfilling inclusion/exclusion criteria after 3 attempts were not allowed to rescreen.

All patients were to have a minimum of 12 clinic visits and 6 scheduled telephone contacts (see [Figure 1](#) and [Figure 2](#)) as follows:

- Visit 1: Screening/inclusion visit (Day 1; coincided with Visit 9/End of Treatment (EOT) in Study A4250-005 for patients in Cohort 1. Assessments that were performed at Visit 9/EOT during Study A4250-005 were not to be repeated.)
- Visit 2: Week 4
 - Telephone contact 1: Week 8
- Visit 3: Week 12
 - Telephone contact 2: Week 18
- Visit 4: Week 22
- Visit 5: Week 24
 - Telephone contact 3: Week 30
- Visit 6: Week 36
 - Telephone contact 4: Week 42
- Visit 7: Week 46
- Visit 8: Week 48
 - Telephone contact 5: Week 54
- Visit 9: Week 60
 - Telephone contact 6: Week 66
- Visit 10: Week 70
- Visit 11: Week 72/optional extension period
- Visit 12: Follow-up visit; Week 76 (for those not participating in optional extension period)
- Optional extension period visits every 16 weeks; Week 88 and onwards

Figure 1 Study Design

[figure not shown]

QD: once daily; T: telephone contact; V: study visit; VS: Visit Screening

Note: Visit 1 coincides with Visit 9 of Study A4250-005. Patients who are not tolerating the 120 µg/kg/day dose may be down-titrated to the 40 µg/kg/day dose following a minimum of 1 week of treatment. The patient can return to the higher dose as soon as deemed appropriate.

This figure is only applicable to Cohort 2 up to Protocol Amendment 5. [Figure 2](#) presents the study design for Cohort 2 as of Protocol Amendment 6.

Figure 2 Study Design for Cohort 2 as of Protocol Amendment 6

QD: once daily; T: telephone contact; V: study visit; VS: Visit Screening

Note: As of Protocol Amendment 6, patients entering Cohort 2 will start treatment at 40 µg/kg/day with the possibility to dose escalate to 120 µg/kg/day after 12 weeks if there is no improvement in pruritus based on investigator judgment. The patient can return to the lower dose if the 120 µg/kg/day dose is not tolerated following a minimum of 1 week of treatment.

Patients were to return to the clinic at Weeks 4 and 12 and thereafter every 10 to 12 weeks for follow-up measurements. Between clinic visits there was to be a telephone contact with the patient and/or caregiver to report AEs. Additional clinic visits may have been required for patients who needed direct site assistance for AE monitoring for safety maintenance and other assessments.

At Visit 11, patients were to be offered the choice to continue receiving odevixibat treatment in an optional extension period. During the optional extension period the patient was to receive odevixibat at the same dose as at the end of the 72-week treatment

period, returning to the clinic every 16 weeks until the drug is commercially available, provided continued use was supported by the risk-benefit profile and the patient had not been previously withdrawn or discontinued from study.

If a patient was prematurely withdrawn from the study prior to Week 72, all assessments scheduled for Visit 11 were to be performed at the time the patient withdrew. If a patient participating in the optional extension study withdrew prior to commercial drug availability, all assessments scheduled for the optional extension period EOT visit were to be performed.

If a liver biopsy was performed according to the local regulations or standard of care at any time during A4250-008, the biopsy results should have been recorded in the electronic case report form (eCRF). If liver biopsy results were collected for a patient in Study A4250-005 or prior to Week 24 in Study A4250-008, the patient was to be asked to consent to a follow-up liver biopsy at Visit 11, if allowed per local regulations, unless 2 prior liver biopsy results had been collected (with at least 1 year between biopsies). Liver biopsies were not performed in Spain.

For patients not participating in the optional extension period, Visit 12 was to take place 28 days after Visit 11. All patients who were prematurely withdrawn were to have this visit 28 days after the last dose of study drug for AE monitoring and other safety follow-up assessments.

If a patient discontinued before Week 72, additional telephone contacts were to be made every 3 months after the Follow-up visit (Visit 12) up to Week 72 to inquire whether the patient had undergone biliary diversion or liver transplantation, and if ongoing TEAEs at the time of discontinuation had resolved. The telephone calls were to take place up until 72 weeks even if the patient had biliary diversion or liver transplant.

Patients and/or caregivers were instructed to complete the electronic diary (eDiary) every morning and evening for the first 24 weeks (Visits 1 to 5) and for the 21 days before each clinic visit thereafter (Visits 6 to 12). In addition, Cohort 2 patients and/or caregivers were instructed to complete the eDiary during the Screening period. Patients participating in the optional extension period were not to complete eDiary entries after Visit 11. The eDiary included patient-reported outcome (PRO) and observer reported outcome (ObsRO) items for evaluation of itching (using PRO), scratching (using ObsRO), and

sleep disturbance (using both PRO and ObsRO). ObsRO in patients of all ages was recorded by a caregiver. If possible, the same caregiver was to complete the ObsRO items throughout the study. Additionally, caregivers were requested to report in the diary the time that study drug was administered during the treatment period.

The study nurse was to monitor eDiary compliance by routine review of the CRF Health website. If both diary entries were missing on a specific day during this time, the study nurse was to call the caregiver/patient with a reminder to complete all scheduled entries. Non-compliance was to be documented and explained in the source documents.

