4.2 Secondary Efficacy Endpoints

The secondary efficacy endpoints include the following:

- **EU and RoW:** Proportion of positive pruritus assessments at the patient level over the 72-week treatment period using the Albireo ObsRO instrument.
- **US:** Change from baseline in fasting serum bile acids after 72 weeks of treatment.
- **All Regions:**

- Change from baseline in serum bile acids at Weeks 4, 12, 22, 24, 36, 46, 48, 60, 70, 72, 76 and all visits (every 16 weeks) during the optional extension period.
- Proportion of individual assessments meeting the definition of a positive pruritus assessment at the patient level using the Albireo ObsRO instrument from Weeks 0-4, Weeks 0-12, Weeks 0-22, Weeks 0-24, Weeks 0-36, Weeks 0-46, Weeks 0-48, Weeks 0-60, and Weeks 0-70, and the proportion of positive pruritus assessments at each 4--week interval between Visit 1/Screening and Visit 5/Week 24, then by each visit between Visit 5/Week 24 and Visit 12/Week 76.
- Proportion of individual AM assessments meeting the definition of a positive pruritus assessment at the patient level using the Albireo ObsRO instrument from Weeks 0-4, Weeks 0-12, Weeks 0-22, Weeks 0-24, Weeks 0-36, Weeks 0-46, Weeks 0-48, Weeks 0-60, Weeks 0-70, and Weeks 0-72, and the proportion of positive pruritus assessments at each 4-week interval between Visit 1/Screening and Visit 5/Week 24, then by each visit between Visit 5/Week 24 and Visit 12/Week 76.
- Proportion of individual PM assessments meeting the definition of a positive pruritus assessment at the patient level using the Albireo ObsRO instrument from Weeks 0-4, Weeks 0-12, Weeks 0-22, Weeks 0-24, Weeks 0-36, Weeks 0-46, Weeks 0-48, Weeks 0-60, Weeks 0-70, and Weeks 0-72, and the proportion of positive pruritus assessments at each 4-week interval between Visit 1/Screening and Visit 5/Week 24, then by each visit between Visit 5/Week 24 and Visit 12/Week 76.
- Number of patients undergoing biliary diversion surgery or liver transplantation. These parameters will be evaluated separately and together at Weeks 24, 48, 72 and all visits (every 16 weeks) during the optional extension period.
- Change in growth from baseline to Weeks 12, 24, 36, 48, 60, 72 and all visits (every 16 weeks) during the optional extension period after initiation of odevixibat treatment, defined as the linear growth deficit (height/length

for age, weight for age, and BMI) compared to a standard growth curve (Z-score, StdDev from the fiftieth percentile, P50).

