9.6.4 Analyses of Secondary Endpoints

All secondary analyses will primarily be summarised descriptively based on the FAS, unless otherwise specified.

The change in secondary endpoints such as serum bile acids, growth, APRI score, Fib-4 score, PELD/MELD will be summarised by visit using descriptive statistics.

❖ Growth

Change in growth (height/length for age, weight for age, mid-arm circumference for age, and BMI for age) will be analysed by using the 1-sample t-test or the Wilcoxon signed

rank test, as appropriate at the end of the 72-week treatment period based on the average of the values at Weeks 70 and 72. In addition, change in growth will also be displayed using graphical presentations. Baseline 1 and 2, defined in the table of derived variables in [Appendix A](#), will be used to calculate change from baseline for data analysis. Baseline 1 will only be used for patients in Cohort 1 who were on odevixibat in Study A4250-005.

The analysis of growth data for height/length, weight, and BMI will be based on calculated values using the software or methods from the Centers for Disease Control and Prevention (CDC) website for patients with age ≥ 2 years old and from the WHO website for patients with age < 2 years old^{7,8}. The analysis of growth data for mid-arm circumference will be based on calculated values for 2 months to 18 years for U.S. Children⁹. CRF collected growth data will be listed.

❖ Serum Bile Acids

For serum bile acids assessments, if a patient has assessments at Weeks 70 and 72, then the average of the 2 assessment values at Weeks 70 and 72 will be used for data analysis. This handling will also be applied to Weeks 22 and 24, and Weeks 46 and 48.

❖ Proportion of Positive Pruritus

The proportion of individual assessments meeting the definition of a positive pruritus assessment at the patient level on the Albireo ObsRO instrument from Weeks 0-4, Weeks 0-12, Weeks 0-22, Weeks 0-24, Weeks 0-36, Weeks 0-46, Weeks 0-48, Weeks 0-60, Weeks 0-70, or the proportion of positive pruritus assessments at each 4-week interval between Visit 1/Screening and Visit 5/Week 24, then by each visit between Visit 5/Week 24 to Visit 12/Week 76 will be summarised descriptively as for the primary analysis for the US. Similar summaries will be provided based on AM scores as well as PM scores.

⁷ <https://www.cdc.gov/nccdphp/dnpao/growthcharts/resources/sas.htm> following CDC's method

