Appendix B: Visit Window

The observation closest to the target day is the measurement used in the analysis for each visit. The following visit window will apply for all laboratory parameters, questionnaires, vital signs, physical measurements and other efficacy parameters in the study, if not otherwise specified.

Table 4: Analysis Visit Window (General)

TIMING OF ASSESSMENT (DAYS RELATIVE TO TREATMENT)	VISIT NAME TO DISPLAY FOR ANALYSIS	TARGET DAY	STUDY DAY (RELATIVE DAY)
Screening (Days -56 to -1)	Baseline		≤ -1
Day 1 Week 1	Baseline		1 (Pre-dose)
Week 4 (± 5 days)	Week 4	28	Post-baseline - 56
Week 12 (± 7 days)	Week 12	84	57–119
Week 22 (± 7 days)	Week 22	154	120–161
Week 24 (± 7 days)	Week 24	168	162–210
Week 36 (± 7 days)	Week 36	252	211–287
Week 46 (± 7 days)	Week 46	322	288–329
Week 48 (± 7 days)	Week 48	336	330–378
Week 60 (± 7 days)	Week 60	420	379–455
Week 70 (± 7 days)	Week 70	490	456–497
Week 72/EOT (± 7 days)	Week 72	504	498–(Last dose day + 14)
4 weeks post last dose of study drug (± 7 days)	Follow-up	28 post last dose	Last dose day + 15–Last dose day + 28
For patients who enter optional extension period:			
Week 72/EOT (± 7 days)	Week 72	504	498– Min(518, start day of optional extension period -1)
Week 88	Week 88	616	Min(519, start day of optional extension period)–672
Week 104, 120, ... (continue every 16 weeks)	Week 104, 120, ... (continue every 16 weeks)	7*week #	(7*(week # - 8) + 1) – Min(7*(week # + 8), Last dose day + 14)

Table 5: Analysis Visit Windows for GIC/GIS, Physical Measurements and Selected Lab Test)

TIMING OF ASSESSMENT (DAYS RELATIVE TO TREATMENT)	VISIT NAME TO DISPLAY FOR ANALYSIS	TARGET DAY	STUDY DAY (RELATIVE DAY)
Screening (Days -56 to -1)	Baseline		≤ -1
Day 1 Week 1	Baseline		1 (Pre-dose)
Week 4 (± 5 days)	Week 4	28	Post-baseline - 56
Week 12 (± 7 days)	Week 12	84	57–126
Week 24 (± 7 days)	Week 24	168	127–252
Week 48 (± 7 days)	Week 48	336	253–420
Week 72/EOT (± 7 days)	Week 72	504	421–(Last dose day + 14)
4 weeks post last dose of study drug (± 7 days)	Follow-up	28 post last dose	Last dose day + 15–Last dose day + 28
For patients who enter optional extension period:			
Week 72/EOT (± 7 days)	Week 72	504	421– Min(518, start day of optional extension period -1)
Week 88	Week 88	616	Min(519, start day of optional extension period)–672
Week 104, 120, ... (continue every 16 weeks)	Week 104, 120, ... (continue every 16 weeks)	7*week #	(7*(week # - 8) + 1) – Min(7*(week # + 8), Last dose day + 14)

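### Extension visits are summarised as a continuation of the Week 4 to 72 series without the same patients' Week 72 values, so a step in the mean after Week 72 can reflect who continued rather than any change in patients

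*SAP*

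**What the plan says.** **Who is in the extension.** Section 3.1 states: "Patients who wished to continue receiving odevixibat after 72 weeks had the option to remain on treatment in an extension period". At Visit 11, "patients were to be offered the choice to continue receiving odevixibat treatment in an optional extension period". Those who enter attend "returning to the clinic every 16 weeks until the drug is commercially available, provided continued use was supported by the risk-benefit profile", and must not have been withdrawn or discontinued earlier.

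**What is reported there.** The bile acid endpoint in Section 4.2 lists Weeks 4 to "60, 70, 72, 76 and all visits (every 16 weeks) during the optional extension period". Growth, APRI, Fib-4 and PELD/MELD (4.2), and liver tests, INR, albumin, blood counts and PedsQL (4.3), are likewise carried into the extension. Section 9.6.4 says: "The change in secondary endpoints such as serum bile acids, growth, APRI score, Fib-4 score, PELD/MELD will be summarised by visit using descriptive statistics". Section 9.6.5 treats the continuous exploratory endpoints the same way. The analysis set is the FAS (Section 7), nothing missing is imputed, and values after biliary diversion or transplantation are dropped (8.1.1).

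**How the visits are built.** In Appendix B, Tables 4 to 6, the extension windows (Week 88, 104, 120 and so on) sit under the line "For patients who enter optional extension period", below Week 72 in the same table.

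**What is not there.** The SAP defines no extension analysis set, no Week 72 reference for continuers, no comparison of continuers with non-continuers and no break in the series at Week 72.

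**The concern.** Up to Week 72, patients are scheduled for every visit. After Week 72 the mean is taken over those who chose to go on, for whom continued use was supported, and who still had no commercial supply. The first two conditions plausibly relate to response, and the third may. The difference between the Week 72 and Week 88 means then has two parts: change within patients, and change in which patients are averaged. Using change from baseline does not remove the second part, because the set of patients contributing changes still differs.

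At stake is how the continuous efficacy data beyond Week 72 are read. The study is meant to describe long-term efficacy, and the Cohort 1 objective is a sustained effect. A further fall in mean bile acids after Week 72 would be read as maintenance or deepening of effect, and a rise as loss of effect. The planned summaries could not tell either from selection.

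**Working it through.** **Plan figure.** The SAP gives no continuation rate, no expected bile acid change and no SD, so there is no plan figure on this point to reproduce. Its only design figure (Section 5, power of 89% to 96% for an event proportion) does not bear on it. All inputs below are assumptions, and every patient's value is held fixed after Week 72.

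**Formula.** Let p be the share continuing, and S and L the mean changes at Week 72 of those who stay and leave.

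- Week 72 mean = p × S + (1 − p) × L
- Week 88 mean = S
- False step = (1 − p) × (S − L)

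**Example.** With p = 0.7, S = −150 and L = −20 µmol/L, the Week 72 mean is 0.7 × (−150) + 0.3 × (−20) = −111. The Week 88 mean is −150. The false step is −39 µmol/L, which is 39/111 = 35% of the Week 72 mean.

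**Range of false improvement.**

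| p | S/L = −150/−20 | S/L = −120/−60 |
|---|---|---|
| 0.6 | 0.4 × 130 = 52 | 0.4 × 60 = 24 |
| 0.7 | 0.3 × 130 = 39 | 0.3 × 60 = 18 |
| 0.8 | 0.2 × 130 = 26 | 0.2 × 60 = 12 |

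**Both directions.** Now let continuation depend on response. Suppose half the patients have a change of −200 and half have 0, so the Week 72 mean is −100.

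| Continue: responders / non-responders | Week 88 mean | False step |
|---|---|---|
| 90% / 90% | −100 | 0 |
| 90% / 60% | 0.45 × (−200) / 0.75 = −120 | −20 |
| 90% / 30% | 0.45 × (−200) / 0.60 = −150 | −50 |
| 60% / 90% | 0.30 × (−200) / 0.75 = −80 | +20 |
| 30% / 90% | 0.15 × (−200) / 0.60 = −50 | +50 |

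The inputs were also varied to 40%, 50% or 60% responders and changes of −200/0 or −150/−20. Apparent improvement is then 12 to 53 µmol/L when responders continue more often (90% against 60% or 30%). Apparent worsening is 12 to 20 µmol/L at 60% against 90%.

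**On an SD scale.** With about 63% to 69% continuing, and logistic selection favouring responders with a slope of 0.5 to 2 per SD, the shift is 0.15 to 0.46 SD.

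**Same patients at both visits.** If the reference is the continuers' own Week 72 mean, the false step is S − S = 0 in every scenario.

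**The case against.** The strongest reply is that these are descriptive, observed-case summaries in an open-label study without formal hypothesis testing, and that the SAP nowhere defines a Week 72 to Week 88 contrast as a result. The n is shown at each visit (9.1), and disposition reports who entered, did not enter and discontinued the extension, with reasons for discontinuing (9.2). That is true and limits the weight of the point. But counts show that numbers fall, not how the leavers had responded.

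A reader might also infer more than the document supports:

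- **That patients leave country by country at launch.** The SAP speaks only of commercial availability and gives no country rule.
- **That the bias favours the drug.** Satisfied responders may be the ones who move to marketed drug. Some poor responders may also be gone before the step: the Week 72 window opens at day 498, and values after surgery or transplantation are excluded.
- **That all efficacy plots run past Week 72.** Section 9.6 promises figures by visit for selected endpoints without saying so. It is nearly explicit only for the liver-test figures in 9.7.2, which cover every post-baseline visit with at least 5 patients in a group. Table and figure templates are in a separate document.
- **That no output shows continuers' Week 72 values.** The individual listings in 9.1 do. What is missing is an aggregate summary.
- **That these are the only efficacy data after Week 72.** Biliary diversion and transplantation are also followed in the extension, with Kaplan-Meier curves censored at last contact (9.6.4).

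These replies narrow the claim. None of them separates composition from change in the by-visit means.

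**Conclusion.** The point holds in a limited form. Selection into the extension is documented, the by-visit observed-case series runs on through it, and no planned summary gives the same patients' Week 72 values. A step in the mean after Week 72 is therefore not interpretable as change in patients.

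The size cannot be derived from the SAP. Under the assumed continuation rates and response means it is roughly 10 to 50 µmol/L for bile acids in either direction, and zero if continuation is unrelated to response. The larger steps need strong selection, such as 90% against 30% continuing, or 40% leaving with a much poorer response.

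The scope is the secondary, exploratory and laboratory by-visit series. Both primary endpoints end at Week 72, and extension patients stop the eDiary at Visit 11, so the primary results and eDiary pruritus are untouched. This is a worthwhile low-cost improvement to the presentation, not an error that undermines the main analysis.

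**What to change.** In Sections 9.6.4 and 9.6.5, for serum bile acids and the other continuous endpoints reported at extension visits (growth, APRI, Fib-4, PELD/MELD, liver tests, PedsQL), add two rows at each extension visit:

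1. The end-of-72-week change from baseline of exactly the patients with a value at that visit. For bile acids, use the Week 70/72 average already defined. State the n, since a patient without an end-of-period value cannot contribute.
2. Their within-patient change from that end-of-72-week value to the visit, with a descriptive 95% CI.

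In any figure that runs past Week 72, break the line there and restart it from the continuers' own Week 72 mean.

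This needs SAP and template wording only, and uses data already collected. The cost is longer tables across the four treatment columns, and small numbers with wide intervals at late visits.
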